## 1.2.4. Overview of Clinical Studies

A total of 32 clinical studies involving over 11,000 subjects have been conducted with tanezumab as of September 2013. Most of these studies were conducted in subjects with osteoarthritis of the knee or hip. A total of 17 clinical studies (4 Phase 2 studies and 13 Phase 3 studies [10 controlled]) were initiated to provide evidence of efficacy and safety of tanezumab with IV (intravenous) or SC administration for the relief of the signs and symptoms of osteoarthritis alone or in combination with NSAIDs. In addition to the osteoarthritis studies, 11 Phase 1/2 studies were conducted to examine the efficacy and safety of tanezumab in other musculoskeletal, neuropathic, and visceral chronic pain conditions, and 2 Phase 2 studies were conducted in cancer subjects with metastatic bone pain. In these studies, tanezumab was administered by IV or SC administration every 8 weeks at fixed doses ranging from 1 mg to 20 mg or equivalent body-weight adjusted doses.

Robust efficacy was demonstrated in osteoarthritis and chronic low back pain studies. Efficacy and safety results observed in non-cancer pain populations are described in the tanezumab investigator brochure, in publically-available documents prepared for the United States (US) Food and Drug Administration (FDA) Arthritis Advisory Committee meeting on March 12, 2012 and in external publications of individual studies.

### 1.2.4.1. Efficacy in Cancer Pain Studies

#### 1.2.4.1.1. Study A4091003

The efficacy of tanezumab in subjects with painful bone metastasis has been evaluated in Study A4091003, which was a randomized, double-blind, placebo-controlled, parallel group study in subjects with cancer pain due to bone metastasis who were receiving background treatment with opioids. In Study A4091003, a total of 59 subjects were treated with either a single IV dose of tanezumab 10 mg (N=29) or placebo (N=30).

A positive outcome for the primary efficacy endpoint for Study A4091003 (ie, the change from Baseline to Week 6 in the daily average pain intensity) was not achieved. Although the mean decrease from Baseline in the tanezumab 10 mg IV treatment group was numerically greater than that for the placebo treatment group, the difference was estimated to be -0.26 (95% CI: -1.18, 0.66) and was not statistically significant (p=0.569).

Post-hoc subgroup analyses indicated that subjects with high Baseline pain scores (>5) in combination with low total weekly opioid use ( $\leq 60.5$  morphine equivalents) may yield the largest treatment difference from placebo. In this subgroup, the estimated treatment difference between tanezumab 10 mg and placebo was -2.72 (95% CI: -5.11, -0.33), and this difference was statistically significant (p=0.027). In another subgroup analysis, subjects with Baseline pain scores >5 (irrespective of Baseline opioid use) had an estimated treatment difference between tanezumab 10 mg and placebo of -1.67 (95% CI: -3.41, 0.08) with p=0.061 when using Baseline Observation Carried Forward (BOCF) imputation at Week 8. Refer to the tanezumab investigator brochure for additional details.

#### **1.2.4.1.2. Study A4091029**

Study A4091029 was a safety extension study designed to investigate the safety and efficacy of tanezumab 10 mg intravenous (IV) in subjects with pain due to bone metastasis who had been randomized and treated in the double-blind parent Study A4091003 and who wished to receive open-label tanezumab therapy.

The change from Study A4091003 Baseline in average pain was maintained up to Week 24 in A4091029 for all subjects. For the 6 subjects who received placebo in Study A4091003, the average pain score in A4091029 subsequently worsened from Week 24 to Week 40 (back to the Study A4091003 Baseline pain level). However for subjects who received tanezumab 10 mg in Study A4091003, the improvement in average pain was further maintained to Week 40 of Study A4091029.

#### **1.2.4.2. Safety in Cancer Pain Studies**

##### **1.2.4.2.1. Study A4091003**

In Study A4091003 (N=59), the incidence of subjects with adverse events was comparable between the tanezumab 10 mg treatment group (62.1%) and in the placebo treatment group (60.0%). One subject in the tanezumab 10 mg treatment group (disease progression; 3.3%) and one subject in the placebo treatment group (embolic stroke; 3.4%) discontinued from the study due to an adverse event. The incidence of serious adverse events was higher in the tanezumab 10 mg treatment group (24.1%) compared with the placebo treatment group (13.3%). Three subjects in total died during the study, 2 (6.9%) in tanezumab 10 mg and 1 (3.3%) in placebo treated subjects. The causes of death for subjects in the tanezumab 10 mg treatment group were disease progression and acute cardiac failure and for the subject in the placebo treatment group the cause of death was disease progression. None of the deaths were considered by the investigator to be related to study medication. Refer to the tanezumab Investigator Brochure for additional details.

##### **1.2.4.2.2. Study A4091029**

In A4091029, (N=41) the incidence of adverse events was comparable to (though marginally greater than) the adverse event incidence for tanezumab-treated subjects in the parent Study A4091003. Nausea was the most common adverse event and is a well-known side effect of opiates which most of the subjects were taking as background analgesia and thus that adverse event was likely caused by the opiates. In addition, the incidence of serious adverse events (including death) and discontinuations due to adverse events was greater in A4091029 than in A4091003, and reflected the progression of the underlying cancer. In A4091029 there were no reported events of osteonecrosis or total joint replacements. Refer to the tanezumab Investigator Brochure for additional details.

#### **1.2.5. Dose Selection Rationale**

In Study A4091003, tanezumab 10 mg administered as a single intravenous infusion in subjects with painful bone metastasis despite background opioid treatment did not demonstrate a significant improvement versus placebo in average daily pain scores at the Week 6 primary endpoint. However, there was evidence of efficacy for tanezumab 10 mg in post-hoc subgroup analyses of subjects with Baseline pain scores >5 and Baseline opioid use

below the median value for the study (60 mg/day in morphine equivalents). Also, in subjects with Baseline pain scores >5 irrespective of Baseline opioid use, a meaningful treatment difference was demonstrated, indicating that it may be possible to demonstrate tanezumab efficacy in subjects with painful bone metastasis under different study conditions.

Within the tanezumab program, there has been a demonstration that different doses of tanezumab may be needed for optimal efficacy, depending on the pain condition under study. For example, tanezumab 10 mg dose levels were needed to achieve comparable levels of efficacy in chronic lower back pain study A4091012 vs 5 mg in Phase 3 osteoarthritis studies. In a small proof of concept study in subjects with painful diabetic neuropathy (A4091031), a single subcutaneous injection of tanezumab 20 mg demonstrated efficacy vs placebo at Week 8. There is no evidence that more frequent dosing would be beneficial in cancer pain compared to other disease states.

The tanezumab 20 mg every 8 weeks dose regimen was studied in Study A4091012. Although it was associated with higher frequencies of adverse events and withdrawals due to adverse events than the lower tanezumab doses, the incidence of serious adverse events was comparable to placebo for all tanezumab doses and tanezumab was considered to be generally safe and well-tolerated in this study. In Study A4091031, tanezumab 20 mg was considered to be generally safe and well tolerated.

Based on the results of the studies noted above there has been precedence for efficacy with the tanezumab 20 mg dose. Because the performance of tanezumab 10 mg in A4091003 was not convincingly robust, the current study will explore the efficacy of tanezumab 20 mg in the population of subjects with painful bone metastasis despite background opioid treatment. Although the primary endpoint is at Week 8, this study has a 24-week double-blind treatment duration to evaluate safety and maintenance of efficacy during 6 months of treatment in this study population.

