### 5.8.1.2. Prohibited Non-opioid Analgesics

The use of analgesics (other than background opioids and permitted uses described in [Sections 5.8.2](#)) is prohibited throughout the study beginning 48 hours (or 5 half-lives, whichever is longer) prior to the start of the Baseline Assessment Period and ending at Week 8.

Use of NSAIDs and COX-2 selective inhibitors, both prescription or over-the-counter (OTC) is prohibited through Week 32 except for occasional use. Management of subjects' NSAID use is described below ([Section 5.8.1.2.1](#)). Intra-articular injection of corticosteroids to any major joint within 30 days prior to the Baseline Assessment Period through Week 32 is prohibited.

Unless the following drugs were started at least 30 days prior to the first day of the Baseline Assessment Period and are maintained at a stable dose, use of concurrent adjuvant analgesics such as single-agent acetaminophen (paracetamol), serotonin norepinephrine reuptake inhibitors (SNRI), tricyclic antidepressants, anticonvulsant medication, corticosteroids, or muscle relaxants is prohibited through Week 8.

Refer to [Appendix 7: Half-Lives of NSAIDs and Other Analgesics](#), for a detailed washout schedule for analgesic medications. Sites must consult product labeling and conduct a taper according to the product instructions if a taper is required.

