#### **5.8.2.2. Permitted Non-opioid Analgesics**

Concurrent adjuvant analgesics such as SNRIs, tricyclic antidepressants, anticonvulsant medication, single-agent acetaminophen (paracetamol)  $\leq 3$  grams/day for 3 days or less per week, corticosteroids, or muscle relaxants are allowed provided these drugs were started at least 30 days prior to start of the Baseline Assessment Period and are maintained at a stable dose through Week 8. With the exception of NSAIDs and intra-articular corticosteroids, standard of care analgesia is permitted starting at Week 8 (refer to [Section 5.8.2.5](#) and [6.3](#)). Use of NSAIDs or intra-articular corticosteroids as part of standard of care analgesia is permitted beginning 16 weeks after the last dose of subcutaneous study medication.

Occasional use of acetaminophen (paracetamol) (eg,  $\leq 3$  grams/day for 3 days or less per week) for pain conditions other than cancer pain is permitted.

In certain circumstances, occasional use of usually-prohibited analgesics (eg, NSAIDs) may be permitted. Such circumstances could include outpatient diagnostic procedures (eg, colonoscopy, dental procedures) or limited accidental injury (eg, ankle sprains, minor fractures, minor burns/sunburns). Refer to [Section 5.8.1](#) for limitations and prohibitions on these analgesics. Subjects should also be counseled to avoid scheduling prospective procedures such that pain medications would be needed within 48 hours of a study visit. Limited use of oral, intramuscular or intravenous corticosteroids for non-analgesic purposes such as prophylaxis or treatment of chemotherapy-induced nausea and vomiting is permitted. However, they must not be taken within 48 hours of a study visit where efficacy assessments are being collected. Topical, inhaled and intranasal corticosteroids are permitted. Contact the assigned study monitor or study clinician for guidance/approval regarding the use of prohibited medications for other self-limiting conditions, accidental injury or other surgical procedures as the extent of the condition, injury or procedure and the resulting pain medication usage may require termination from the study.

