## **6.2.2. Double Blind Treatment Period**

### **6.2.2.1. Background Opioid Use**

After randomization and through Week 8, all subjects will continue to take the opioid regimen or morphine equivalent dose used during the Baseline Assessment Period. The average of the total daily opioid doses (ATC + IR) taken during the Baseline Assessment Period will be used as the Baseline total daily opioid dose.

Beginning on Day 1 and through Week 8, the average total daily dose of opioids between study clinic visits should not exceed the Baseline total daily morphine equivalent opioid dose by more than 10%. Subjects who require an opioid dose more than 10% greater than the Baseline total daily opioid dose should discontinue the Double-Blind Treatment Period for insufficient clinical response or disease progression ( per investigator's judgment) and enter the 6-month Safety Follow-Up period (refer to [Section 6.4](#)). Opioid dose reduction will be allowed if the subject experiences intolerable opioid side effects, if pain decreases or if the subject requests dose reduction. Once reduced, the opioid dose may be re-increased if needed for pain relief, but should not exceed the Baseline total daily morphine equivalent opioid dose by more than 10%.

Following the Week 8 clinic visit, subjects will remain on the opioid regimen used during the Baseline Assessment Period but will be allowed to change formulation, increase or decrease the amount of their background opioid medication without restriction if the investigator

considers such changes are necessary. Opioid reductions and increases will be done using accepted clinical guidelines (refer to [Section 6.1.1.2.4](#)).

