### 9.2.2. Secondary Efficacy Endpoint Analysis

Unless otherwise stated, all data up to Week 24 will be summarized, and data for the specified time points up to Week 24 will be analyzed.

The change from Baseline for the daily average and worst pain intensity in the bone metastasis index cancer pain site will be summarized for each week from 1 to 24. The change from Baseline to Weeks 1, 2, 4, 6, 8 (Worst Pain), 12, 16 and 24 will be analyzed using analysis of covariance (ANCOVA) as described above, using multiple imputation.

A secondary analysis for the change from Baseline in the daily average pain scores will use a repeated measures mixed effects model, on the available data over Weeks 1 to 24. Estimates for treatment groups and treatment difference for Weeks 1, 2, 4, 6, 8, 12, 16 and 24 will be shown. Additional secondary analysis for the change from Baseline to Week 8 and 16 in the daily average pain will use single imputation Last Observation Carried Forward (LOCF) and Baseline Observation Carried Forward (BOCF) for missing data.

The mean of the subject's average and worst pain in the non-index cancer sites, over all non-index sites (for up to 2 sites per subject) and for visceral non-index cancer sites will be calculated for Baseline and for each week, and for the change from Baseline. The change from Baseline to Weeks 1, 2, 4, 6, 8, 12, 16 and 24 in average and worst pain in the non-index cancer pain sites will be analyzed using analysis of covariance (ANCOVA) as described above, using multiple imputation. An additional analysis will utilize only those sites where Baseline average/worst pain is at least 5. If a subject has no nominated non-index sites (first analysis) or no nominated non-index sites where Baseline is at least 5 (second analysis) then that subject would be excluded from the respective analysis.

Additional ANCOVA analyses with multiple imputation for the primary endpoint will be used to examine the interaction of treatment group with study site, Baseline pain score, type of primary cancer (eg, breast, lung, etc), Baseline opioid use and the stratification parameters.

The change from Baseline to Weeks 2, 4, 8, 16, and 24 in the CCI [REDACTED] will also be summarized, and analyzed using the ANCOVA main effects model as described above with multiple imputation.

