Chemotherapy (see below for criteria regarding biologics)	Allowable, with some exceptions (see Section 5.8.2.3.), if ongoing for at least 30 days before start of Baseline Assessment Period.	If a new chemotherapy regimen is required prior to Week 8, subject should be withdrawn and entered in the Early Termination Follow-Up period (refer to Section 6.4).  Chemotherapies associated with peripheral neuropathy (i.e. paclitaxel, docetaxel, oxaliplatin, cisplatin, vincristine, thalidomide and bortezomib) are not permitted from 30 days prior to the first day of the Baseline Assessment Period to Week 48 regardless of symptomatology .
Radiopharmaceutical treatment or radiotherapy for bone metastasis	Permitted if $\geq 30$ days prior to first day of the Baseline Assessment Period.	Prohibited within 30 days of the first day of the Baseline Assessment Period through to Week 8.  If initiation of radiotherapy to sites of bone metastasis or new radiopharmaceutical regimen is required prior to Week 8, subject should be withdrawn and entered in the Early Termination Follow-Up period (refer to Section 6.4).
Concomitant hormonal anti-cancer treatment (eg, GnRH agonists or antagonists, anti-androgens or anti-estrogens)	Permitted if ongoing at stable dose for $\geq 30$ days prior to first day of Baseline Assessment Period.	Post-Baseline, should remain stable until at least Week 8.  If initiation of new concomitant

		hormonal anti-cancer treatment is required prior to Week 8, subject should be withdrawn and entered in the Early Termination Follow-Up period (refer to Section 6.4).
--	--	---

\*Following the Week 8 visit, standard of care treatments may be initiated (refer to Section 5.8.2.3).

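### The Week 12, 16 and 24 pain analyses estimate an effect under freely adjusted background treatment and cannot, by themselves, separate a maintained tanezumab effect from rescue

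*Protocol*

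**What the plan says.** **Purpose.** Protocol Section 1.2.5 places the primary endpoint at Week 8 and explains the longer period as a "24-week double-blind treatment duration to evaluate safety and maintenance of efficacy during 6 months of treatment in this study population". Section 2.2.2.1 lists index-site pain and responder endpoints at Weeks 12, 16 and 24 as secondary.

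**Up to Week 8.** Section 6.2.2.1 sets a margin of 10%: "the average total daily dose of opioids between study clinic visits should not exceed the Baseline total daily morphine equivalent opioid dose by more than" this margin. A subject who needs more should discontinue double-blind treatment. For radiotherapy to bone metastasis, Appendix 8 says: "Prohibited within 30 days of the first day of the Baseline Assessment Period through to Week 8". Section 5.8.1.3 withdraws from study treatment a subject whose progression requires it before then.

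**After Week 8.** If the investigator considers it necessary, subjects may "increase or decrease the amount of their background opioid medication without restriction" (Section 6.2.2.1). Section 5.8.2.2 adds: "With the exception of NSAIDs and intra-articular corticosteroids, standard of care analgesia is permitted starting at Week 8". Use of NSAIDs "is prohibited through Week 32 except for occasional use" (Section 5.8.1.2). Appendix 8 states: "Following the Week 8 visit, standard of care treatments may be initiated". Sections 5.8.1.3, 5.8.2.6 and 6.2.2.2 require the study clinician to be told of new or changed cancer or bone-metastasis treatment between Weeks 8 and 32, and to advise whether the subject should leave study treatment.

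**Analysis.** Section 9.2.2 says of index-site average and worst pain: "The change from Baseline to Weeks 1, 2, 4, 6, 8 (Worst Pain), 12, 16 and 24 will be analyzed". The method is the Section 9.2.1 ANCOVA with multiple imputation. A repeated measures model on available data to Week 24, LOCF and BOCF analyses, and logistic models for response are also planned.

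**The concern.** The conditions under which pain is measured change at Week 8, but the analysis does not. Take a subject whose pain control fails. Before Week 8, a need for more than the permitted opioid margin takes the subject off double-blind treatment. If this is recorded as lack of efficacy and the Week 8 data are missing, Section 9.2.1 imputes around that subject's Baseline. After Week 8 the same subject may have opioids raised or another analgesic added and remain on study treatment. The lower score that follows is then used as observed at Weeks 12, 16 and 24.

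Two misreadings become possible. If more placebo subjects intensify, the pain difference shrinks and a maintained effect can look lost. If more tanezumab subjects intensify as the drug effect fades, their pain still looks controlled and a lost effect can look maintained. The parts of the pain curve before and after Week 8 also measure different things.

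**Working it through.** **1. The plan's own figure.** Section 9.1 gives a target difference of -1.0, SD 2.0, two-sided 5% and 85% power. With z-values 1.960 and 1.036, n = 2 x (1.960 + 1.036)^2 x 2.0^2 / 1.0^2 = 71.8, so 72 per group. This reproduces the stated size, and nothing in it is disputed.

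**2. What triggers imputation.** Multiple imputation in Section 9.2.1 acts on missing values, with a rule that depends on why they are missing. LOCF and BOCF in Section 9.2.2 also fill only missing values, and the repeated measures model uses available data. In the visible text, no rule covers a score that was recorded after added analgesia or radiotherapy.

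**3. Size of the distortion.** Let D be the tanezumab-minus-placebo difference without intensification, pP and pT the shares intensifying on placebo and tanezumab, and r the points by which intensification lowers a subject's pain score (taken as equal in both arms). Each arm's mean falls by p x r, so

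observed difference = D + (pP - pT) x r.

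The chance of a significant result favouring tanezumab, with 72 per group and no dropout, uses SE = 2.0 x sqrt(2/72) = 0.333 and is approximately Phi(|observed| / 0.333 - 1.96).

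D = -1.0 and SD = 2.0 are the protocol's Week 8 design values, carried forward. All values of pP, pT and r, and D = 0 in the last row, are assumptions.

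| D | pP | pT | r | Observed difference | Chance of significance |
|---|---|---|---|---|---|
| -1.0 | equal to pT | equal to pP | any | -1.00 | 85% |
| -1.0 | 30% | 20% | 1.5 | -1.0 + 0.10 x 1.5 = -0.85 | 72% |
| -1.0 | 40% | 20% | 1.5 | -1.0 + 0.20 x 1.5 = -0.70 | 56% |
| -1.0 | 40% | 20% | 2.0 | -1.0 + 0.20 x 2.0 = -0.60 | 44% |
| -1.0 | 50% | 25% | 2.0 | -1.0 + 0.25 x 2.0 = -0.50 | 32% |
| 0 | 20% | 40% | 2.0 | 0 - 0.20 x 2.0 = -0.40 | 22% |

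The middle rows show a fully maintained effect being diluted. The last row shows the reverse: an effect that has vanished appears as -0.40 and reaches significance in tanezumab's favour about 22% of the time, against 2.5% with no true difference and no distortion. With equal rates and equal r the mean difference is not distorted.

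**The case against.** Several points on the other side are sound and limit the concern.

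- **Not everything is released.** NSAIDs and intra-articular corticosteroids stay restricted to Week 32, beyond the last pain endpoint. New bone-metastasis treatment goes to the study clinician and may end study treatment. Section 6.4 also withdraws subjects without acceptable relief throughout the double-blind period. A reader might infer that all co-treatment is simply freed at Week 8, and the documents do not say that. But withdrawal for new treatment is decided case by case, opioid and other analgesic changes need no such consultation, and the allowable opioid regimen has no ceiling after Week 8.
- **The comparison is still valid for what it estimates.** It remains randomized and blinded. Opioid consumption and rescue doses are analysed separately (Section 9.3.4). A lasting pain difference without higher opioid use on tanezumab would support maintenance. A reader might infer that Weeks 12 to 24 can show nothing about maintenance, which goes too far. The opioid tables are, however, not combined with the pain scores and do not cover radiotherapy or non-opioid analgesics.
- **Failure before Week 8 is not always imputed as failure.** Withdrawal before Week 8 for a higher opioid need or for radiotherapy may be recorded as disease progression. Unless it is also coded as an adverse event, Section 9.2.1 then imputes around the last observed value, not Baseline. A reader might infer that every such case counts as failure at Week 8. Only cases coded as lack of efficacy, adverse event or death are imputed that way.
- **The SAP or redacted text may add a rule.** Section 9 lets the SAP modify the plan, and parts of the efficacy section are blacked out, so a rule may exist elsewhere. But the visible Section 9.2.2 fixes the models, time points and imputation, and the tension is with a purpose stated in the same protocol.
- **Maintenance is not a formal objective.** It appears in the rationale and is reflected in secondary endpoints, not in Sections 2.1.1 or 2.1.2. That limits the weight of the point without removing it.

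**Conclusion.** The concern holds in a limited form. The Week 12, 16 and 24 pain and responder analyses estimate the effect of tanezumab when background treatment is freely adjusted. That is a legitimate quantity, but alone it does not answer the maintenance question in Section 1.2.5, because a score kept low by the drug and one kept low by rescue enter identically.

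The size is unknown because the documents give neither intensification rates nor their effect on pain. Under the assumed scenarios a true -1.0 appears as -0.85 to -0.50, and a vanished effect could appear as -0.40. These are illustrations: they assume one common effect of intensification, the Week 8 SD, and 72 per group with no dropout. They do not predict which direction would occur. The Week 8 primary analysis and its sample size are unaffected.

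**What to change.** Keep every care rule and every planned analysis. Add to Section 9.2.2 one pre-specified supplementary analysis of index-site average pain, worst pain and response at Weeks 12, 16 and 24.

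- **Trigger, for analysis only:** an opioid dose more than 10% above Baseline, averaged over several weekly diary entries (the margin Section 6.2.2.1 already uses before Week 8); a new analgesic for cancer pain; or radiotherapy to the index site.
- **Handling:** scores after the trigger are treated as Section 9.2.1 treats discontinuation for lack of efficacy, and as non-response for the responder endpoints.
- **New systemic anticancer treatment:** report it separately. Counting it as analgesic failure would mix tumour progression with loss of analgesic effect.
- **Reporting:** show the share intensified by arm and week, state that the existing analyses estimate the effect under adjusted background treatment, and interpret any maintenance statement in light of both analyses.

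The cost is about one paragraph and one extra set of tables. Opioid diaries run to Week 24 (Section 7.1.2), and standard-of-care use goes on the concomitant medication CRF (Table 1, footnote q). The sponsor should confirm that radiotherapy dates and sites are captured. The downsides are that the added analysis is more conservative, and that one 24-hour opioid recall per week after Week 8 makes the trigger approximate, which is why it should average several entries.
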